7 MEASUREMENTS OF TREATMENT COMPLICANCE

Due to the method of administration of the treatments, compliance will be examined in terms of completed doses, where one dose will be considered as one complete treatment administration (ie, three injections).

Treatment compliance will be calculated as:

total number of completed doses
$$total number of expected doses$$
 $total number of expected doses$ $total number of expected doses$

where the total number of expected doses is derived relative to when the subject finishes treatment. If a subject completes treatment nine doses are expected (three each at Baseline, Week 4 and Week 8). If a subject discontinues early, then the number of expected injections is based on the time of early discontinuation relative to the dosing visits.

A summary of percent treatment compliance categorized as ≤75% and >75% will be provided by treatment group.

A by-subject listing of treatment compliance will be provided.

EFFICACY ANALYSES 8

Statistical analysis of the primary efficacy variable 8.1

Derivations of PASI score and response 8.1.1

PASI scoring of psoriatic plaques is based on three criteria: redness (R), thickness (T), and scaliness (S). Severity is rated for each index (R, S, T) on a 0-4 scale (0 for no involvement up to 4 for very marked involvement). The body is divided into four areas comprising the head (h), upper extremities (u), trunk (t), and lower extremities (l). In each of these areas, the fraction of total surface area affected is graded on a 0-6 scale (0 for no involvement; up to 6 for 90% - 100% involvement).

The various body regions are weighted to reflect their respective proportion of BSA. The composite PASI score is then calculated by multiplying the sum of the individual-severity scores for each area by the weighted area-of-involvement score for that respective area, and then summing the four resulting quantities as follows (note for R, T, and S scores are as follows: 0 = none, 1 = slight, 2 = moderate, 3 = marked, and 4 = very marked):

$$PASI = (0.1 \times (R_h + T_h + S_h) \times A_h) + (0.2 \times (R_u + T_u + S_u) \times A_u) + (0.3 \times (R_t + T_t + S_t) \times A_t) + (0.4 \times (R_l + T_l + S_l) \times A_l)$$
(4)

where

 R_h , R_u , R_t , R_l = redness score of plagues on the head, upper extremities, trunk, and lower extremities, scored 0-4 respectively;

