Confidential Page 25 of 63 T_h , T_u , T_t , T_l = thickness score of plaques on the head, upper extremities, trunk, and lower extremities, scored 0-4 respectively;

 S_h , S_u , S_t , S_l = scaliness score of plaques on the head, upper extremities, trunk, and lower extremities, scored 0-4 respectively;

 A_h , A_u , A_t , A_l = numerical value translation of % area of psoriatic involvement score for the head, upper extremities, trunk, and lower extremities, respectively (where 0 = 0% [clear], 1 = >0% to <10%, 2 = 10% to <30%, 3 = 30% to <50%, 4 = 50% to <70%, 5 = 70% to <90%, and 6 = 90% to 100%).

The highest potential PASI score is 72 for severe disease; the lowest is 0 for no psoriasis lesion. PASI scores are treated as a continuous score, with 0.1 increments within these values. The percent improvement in PASI scores from Baseline will be computed as:

Percent improvement from Baseline =
$$100 \times \frac{Baseline PASI - Post Baseline PASI}{Baseline PASI}$$
 (5)

If a subject has experienced an improvement, this measure will be positive. If a subject has experienced a worsening in their condition, this measure will be negative.

If a subject is missing 1 or 2 severity measurements for a certain region, the average of the remaining severity measurement(s) within that region will be utilized to substitute for the missing severity measurement(s) in that region. If the area of affected skin and/or all severity measurements for up to 2 regions are missing, then the missing (R+T+S) x A for a region will be substituted by the average of the available (R+T+S) x A. Otherwise, the PASI will be set to missing.

A categorical variable, PASI90, is defined to be equal to 1 if the percentage improvement from Baseline in the PASI scores is 90% or greater and 0 if the percentage improvement from baseline is less than 90%. This definition is introduced for the purpose of identifying subjects who respond to the treatment (1 = responder, 0 = non-responder). Similarly, the categorical secondary efficacy variables PASI50, PASI75, and PASI100 response are equal to 1 for subjects with improvements of 50% or greater, 75% or greater and 100% from Baseline in PASI score, respectively (and equal to 0 otherwise),

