8.1.2 Primary analysis of the primary efficacy variable

The primary efficacy variable will be analyzed for all subjects in the FAS.

The number and percentage of subjects achieving a PASI90 response (as defined in Section § 7.1) at Week 12 will be presented by treatment group.

The dose-response relationship between treatment and PASI90 response will be assessed to test the following hypotheses:

$$H_0: -2\mu_1 - \mu_2 + 0\mu_3 + \mu_4 + 2\mu_5 = 0$$

$$H_1$$
: $-2\mu_1 - \mu_2 + 0\mu_3 + \mu_4 + 2\mu_5 \neq 0$

where 1 = placebo, 2 = bimekizumab 64mg Q4W, 3 = bimekizumab 160mg Q4W, 4 = bimekizumab 320mg Q4W, and 5 = bimekizumab 480mg Q4W.

This will be done by using a logistic regression model which will include fixed effects for treatment, region (see Section 4.8), and prior biologic exposure (yes/no). This will be evaluated using a linear contrast in which equal spacing between each of the doses is assumed.

The coefficients for this linear contrast will be -2, -1, 0, 1 and 2 for placebo, bimekizumab 64mg Q4W, bimekizumab 160mg Q4W, bimekizumab 320mg Q4W, and bimekizumab 480mg Q4W, respectively. While the bimekizumab 320mg loading dose followed by bimekizumab 160mg Q4W has been left out of the linear contrast for evaluating dose response, it will remain a part of the logistic regression model and will be compared to the bimekizumab 160mg Q4W dose as a secondary analysis of the primary efficacy variable.

If the logistic regression model is unable to converge, then prior biologic exposure will be dropped from the model to facilitate convergence. If convergence is not obtained after dropping prior biologic exposure, then region may be dropped from the model. The linear contrast from the logistic regression model will be evaluated at a two-sided significance level of α =0.05.

NRI will be used to account for missing data; ie, subjects with a missing PASI score at Week 12 or who discontinued study treatment prior to the Week 12 Visit will be considered non-responders for the primary analysis.

The results produced in the SAS modelling process for the primary endpoint will be provided as a supportive output.

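### The PASI missing-data rule in SAP 8.1.1 has no exception for a region graded clear, so blank severities there can replace a known zero or void the score

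*SAP*

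**What the plan says.** SAP 8.1.1 (Derivations of PASI score and response) builds the PASI from four regional products, (R+T+S) x A, weighted 0.1, 0.2, 0.3 and 0.4 for head, upper limbs, trunk and lower limbs. Area grades are defined "where 0 = 0% [clear], 1 = >0% to <10"% and so on up to 6. For severity: "Severity is rated for each index (R, S, T) on a 0-4 scale (0 for no involvement up to 4 for very marked involvement").

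The region-level missing-data rule has three parts:

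- Trigger: "If the area of affected skin and/or all severity measurements for up to 2 regions are missing"
- Substitution: "then the missing (R+T+S) x A for a region will be substituted by the average of the available (R+T+S) x A"
- More than two regions: "Otherwise, the PASI will be set to missing"

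PASI90 is then "equal to 1 if the percentage improvement from Baseline in the PASI scores is 90% or greater". Under SAP 8.1.2, "subjects with a missing PASI score at Week 12 or who discontinued study treatment prior to the Week 12 Visit will be considered non-responders" in the primary analysis.

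Neither SAP 8.1.1 nor Protocol 9.1 with Table 9–1 says what to do when a region's area is recorded as 0 and its severities are blank.

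**The concern.** When A = 0 the product (R+T+S) x A is 0 for any severities, so nothing about that region is unknown. The trigger, however, is joined by and/or: blank severities alone are enough, even with the area on record. A programmer following the text would replace a known zero or void the score.

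Blanks in clear regions are plausible. Protocol 9.1 has the investigator grade the lesions in each area, and a clear region has none. The SAP deals with the parallel situation for other instruments: an unaffected nail adds nothing to the mNAPSI (SAP 8.3.6), and a DLQI item marked not relevant scores 0 (SAP 8.3.4). The primary instrument has no such provision.

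At stake are PASI90 at Weeks 8 and 12, PASI75, PASI100 and time to response, all of which use this derivation. Clear regions after Baseline occur mainly in responders, so post-baseline errors would fall mainly on them.

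**Working it through.** **The plan's own figure.** SAP 2.4 states >99% power for a linear trend, with 40 per arm and rates of 2, 20, 40, 50 and 60%. With scores −2 to 2:

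- d = −2(0.02) − 0.20 + 0 + 0.50 + 2(0.60) = 1.46
- Null SE = √(0.344 × 0.656 × 10/40) = 0.2375
- Alternative SE = √(1.4484/40) = 0.1903
- z = (1.46 − 1.96 × 0.2375)/0.1903 = 5.23, so power is above 99.99%. The figure reproduces.

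**The rule applied to Week 12 states.** In this table a × b means severity sum × area grade. All clear regions are blank except in the last row. The entry minimum for Baseline PASI is 12 (SAP 2.3.1). NR = non-responder through NRI.

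| State | True PASI | Literal rule | Improvement, Baseline 12 | Improvement, Baseline 20 |
|---|---|---|---|---|
| Trunk 1×1, lower 2×1 | 1.1 | 1.55 | 90.8% → 87.1% | 94.5% → 92.25% |
| Head 2×1, upper 2×1 | 0.6 | 2.0 | 95.0% → 83.3% | 97.0% → 90.0% |
| Trunk 1×1, lower 1×1 | 0.7 | 1.0 | 94.2% → 91.7% | 96.5% → 95.0% |
| Lower 2×1 only | 0.8 | missing | 93.3% → NR | 96.0% → NR |
| All four clear, all blank | 0 | missing | 100% → NR | 100% → NR |
| All four clear, one or two blank, rest entered as 0 | 0 | 0 | 100%, unchanged | 100%, unchanged |

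First row in full: the true score is 0.3×1 + 0.4×2 = 1.1. The two blanks each take (1+2)/2 = 1.5, which adds (0.1+0.2)×1.5 = 0.45 and gives 1.55. PASI90 is kept from Baseline 1.55/0.10 = 15.5 upwards.

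**How often averaging flips a state.** I enumerated severity sums of 1–6 and area grades of 0–2 in each region and kept the states that truly meet PASI90.

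| Baseline PASI | One clear region: flipped | Two clear regions: flipped |
|---|---|---|
| 12 | 96 of 104 | 135 of 141 |
| 20 | 589 of 768 | 303 of 363 |

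These are unweighted arithmetic states, not proportions of patients. With three or four blank clear regions every state is voided.

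**The opposite direction at Baseline.** Head clear and blank, upper limbs 6×2, trunk 6×3, lower limbs 6×3. The true score is 0.2×12 + 0.3×18 + 0.4×18 = 15.0. The head takes (12+18+18)/3 = 16, adding 1.6, so the score becomes 16.6. The PASI90 cut-off then rises from 1.50 to 1.66, which makes response easier.

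**Illustrative effect on power.** Assume a share f of responders is lost in every arm. The documents give no value for f.

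| f | Trend in proportions | Logistic contrast, Wald approximation | 64 mg vs placebo |
|---|---|---|---|
| 0 | >99.99% | 98.6% | 73.9% |
| 25% | 99.98% | 92.0% | 59.6% |
| 50% | 98.3% | 73.7% | 42.1% |

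The first column is the test used for the sample size. The second approximates the contrast specified in SAP 8.1.2. It is rough, because at f = 0 the placebo arm (0.8 expected responders) supplies 5.10 of its total variance of 5.77.

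**Sensitivity analyses (SAP 8.1.4).** All use the same derived PASI. The Week 12 de facto analysis applies NRI to a voided score, multiple imputation imputes over it, and the observed-values analysis drops the subject. None restores the known value.

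**The case against.** The strongest reply is that the trigger may never occur. Protocol 9.1 and SAP 8.1.1 both give severity an explicit zero category, so a clear region has a valid entry of R = T = S = 0. No passage shows that blanks are expected, and Protocol 13.3.2 plans computerised checks and manual review that could query them. This stands as a limit on frequency. It does not close the gap, because none of these passages requires the zeros for PASI.

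A second reply is that the rule replaces a missing product, and a product with A = 0 is not missing. SAP 8.1.1 also says that the lowest score, 0, means no lesion, which sits badly with voiding a clear subject. That reading is sensible, but the trigger is worded on missing measurements, so the text leaves it to the programmer.

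A third is that multiple imputation and the observed-values analysis do not count a voided on-treatment score as non-response. That is correct for voiding, but neither addresses the averaging route.

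A reader might also infer more than the documents support:

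- That near-clear subjects will in fact be turned into non-responders. eCRF practice is not shown, so this is conditional.
- That every blank gives a wrong value or a lost response. The average runs over all available regions, including recorded zeros, so a fully clear subject with one or two blanks still scores 0. Other states change score but keep PASI90.
- That the bias runs only against response. Blanks at Baseline can work the other way.

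**Conclusion.** The gap is real and lies on the primary endpoint. Read literally, SAP 8.1.1 gives a wrong or missing PASI in an identifiable case where the correct contribution is known. Everything beyond that depends on severities being left blank in regions graded 0, whose frequency is unknown and may be nil.

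Where it happens, one or two blank clear regions can, but need not, change response status. Three or four always void the score, and at Week 12 this makes the subject a non-responder, including for PASI100 when fully clear. The net direction cannot be fixed from the documents, although post-baseline errors would fall mainly on responders.

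The trend test behind the sample size is robust even to large assumed losses. The logistic contrast keeps about 92% power at an assumed 25% loss, on a rough approximation. More exposed are the estimated response rates, PASI100 and the low end of the fixed sequence: 64 mg versus placebo falls from 73.9% to 59.6% power at the same assumed loss. The documents do not support a claim that the primary conclusion is in danger. They do support a clarification.

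**What to change.** Add to SAP 8.1.1, before the substitution rule:

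> If the area score of a region is 0, that region contributes 0 whether or not severities are recorded. A region counts as missing only if its area is missing, or if its area is >0 and all three severities are missing.

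Apply it at Baseline and at all post-baseline visits, so that numerator and denominator of the percent improvement are treated alike. The cost is this short addition and one line of code. Provided that the recorded area of 0 is itself right, the change cannot make a score less accurate, because it only puts a known value in place of an imputed or voided one. If the eCRF already forces or fills in zeros, no result changes and the intent is documented.

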8.1.2 Primary analysis of the primary efficacy variable

The primary efficacy variable will be analyzed for all subjects in the FAS.

The number and percentage of subjects achieving a PASI90 response (as defined in Section § 7.1) at Week 12 will be presented by treatment group.

The dose-response relationship between treatment and PASI90 response will be assessed to test the following hypotheses:

$$H_0: -2\mu_1 - \mu_2 + 0\mu_3 + \mu_4 + 2\mu_5 = 0$$

$$H_1$$
: $-2\mu_1 - \mu_2 + 0\mu_3 + \mu_4 + 2\mu_5 \neq 0$

where 1 = placebo, 2 = bimekizumab 64mg Q4W, 3 = bimekizumab 160mg Q4W, 4 = bimekizumab 320mg Q4W, and 5 = bimekizumab 480mg Q4W.

This will be done by using a logistic regression model which will include fixed effects for treatment, region (see Section 4.8), and prior biologic exposure (yes/no). This will be evaluated using a linear contrast in which equal spacing between each of the doses is assumed.

The coefficients for this linear contrast will be -2, -1, 0, 1 and 2 for placebo, bimekizumab 64mg Q4W, bimekizumab 160mg Q4W, bimekizumab 320mg Q4W, and bimekizumab 480mg Q4W, respectively. While the bimekizumab 320mg loading dose followed by bimekizumab 160mg Q4W has been left out of the linear contrast for evaluating dose response, it will remain a part of the logistic regression model and will be compared to the bimekizumab 160mg Q4W dose as a secondary analysis of the primary efficacy variable.

If the logistic regression model is unable to converge, then prior biologic exposure will be dropped from the model to facilitate convergence. If convergence is not obtained after dropping prior biologic exposure, then region may be dropped from the model. The linear contrast from the logistic regression model will be evaluated at a two-sided significance level of α =0.05.

NRI will be used to account for missing data; ie, subjects with a missing PASI score at Week 12 or who discontinued study treatment prior to the Week 12 Visit will be considered non-responders for the primary analysis.

The results produced in the SAS modelling process for the primary endpoint will be provided as a supportive output.

8.1.3 Secondary analyses of the primary efficacy variable

As a supportive analysis for the primary efficacy variable, the same logistic regression model described in Section 8.1.2 will be used to assess the effect of each individual dose vs placebo on PASI90 response. Comparisons will be made for each dose vs placebo at a two-sided significance level of α =0.05. For each dose, the odds ratio vs placebo, the 95% confidence interval, and the corresponding p-value will be calculated.

The pairwise comparisons of bimekizumab versus placebo will be formally evaluated for statistical significance only if the primary dose response efficacy analysis is statistically significant. Once the dose response has been established, pairwise testing of each bimekizumab dose versus placebo will account for multiplicity by using a fixed sequence testing procedure with each bimekizumab dose being tested sequentially from the highest dose to the lowest dose. Each test will only be conducted if the previous test reaches significance at a two-sided significance level of α =0.05. This procedure will control the overall Type I error rate. While formal evaluation of statistical significance will only proceed as described above, the p-values for all pairwise tests vs placebo will be provided, regardless of whether or not the testing procedure was completed for all bimekizumab doses.

A pairwise comparison will also be made for the bimekizumab 160mg Q4W group versus the bimekizumab 320mg loading dose followed by bimekizumab 160mg Q4W group, but this evaluation will not be part of the sequential testing procedure described above (ie, the p-value will be nominal).

The results produced in the SAS modelling process for the secondary analyses of the primary efficacy variable will be provided as a supportive output.

8.1.4 Supportive and sensitivity analyses of the primary efficacy variable

8.1.4.1 Sensitivity analyses

The primary dose response analysis and pairwise comparisons will be repeated for all subjects in the PPS to evaluate the effect of important protocol deviations on the analysis.

An ordered categorical analysis using a non-parametric correlation statistic of Mantel and Haenszel and modified ridit scores will be performed as a sensitivity analysis to the primary dose-response evaluation based on the logistic regression model. This analysis will include region and prior biologic exposure as stratification factors to adjust for potential differences in the dose response based on these variables, and will be evaluated at a 2-sided significance level of α =0.05.

Sensitivity analyses for the primary dose response analysis of the primary efficacy variable, designed to evaluate the assumptions related to the handling of missing data are as follows:

- 1. An analysis will be performed in which all available data at Week 12 will be considered. This analysis will be based on the logistic regression model to evaluate dose-response as specified in the primary analysis (see Section 8.1.2). However, in this case, subjects will be analyzed according to their randomized treatment, even if they discontinued prior to Week 12 and were no longer on the randomized study treatment when the assessment was performed at Week 12. Even though efforts will be made to collect the primary outcome data for all subjects at Week 12, there may still be some subjects for whom Week 12 efficacy data cannot be obtained. In this case, NRI will be used for these subjects. For the purposes of analyses these will be referred to as "Week 12 de facto analysis". The estimand here is the difference in outcome improvement at the planned endpoint for all randomized participants (Mallinckrodt, 2012). This is an estimand of effectiveness to evaluate the de facto hypothesis. It should be noted that this measures something different from the primary analysis and could be confounded by placebo subjects who withdraw and are subsequently on another active medication at the time of the Week 12 assessment. Therefore, the results of this analysis should be interpreted in the appropriate context.

- 2. For each complete imputed data set, the dichotomous responder rate based on the PASI scores will be computed. Each complete imputed data set will then be analyzed based on a logistic regression model with factors of treatment group, region, and prior biologic exposure.
 - Note: For derivation of PASI90 response, the PASI value at Week 12 in the imputed data sets will be compared directly to the observed Baseline PASI value to determine whether or not a reduction of at least 90% was achieved. If values outside of the pre-defined range of values for PASI (0-72) are imputed, they will be cut off as appropriate after the multiple imputation procedure but before deriving the responder variable. For example, an imputed PASI value of -0.5 would be changed to 0 before deriving the PASI90 responder variable.
- 3. The Week 12 results from the logistic regression analysis of each of the 100 imputed data sets will be combined for overall inference using Rubin's rules, which account for the uncertainty associated with the imputed values (Rubin, 1987). This will be done using SAS PROC MIANALYZE.

Some key points to consider relative to the calculation of the odds ratios and corresponding confidence intervals are noted below:

As the estimates of the odds ratios from the logistic regression model in step 3 follow a lognormal distribution, a log transformation is needed to normalize these estimates since the procedures for combining results from multiple imputed datasets are based on the assumption that the statistics estimated from each imputed dataset are normally distributed. Therefore, the log of the odds ratio estimates from the logistic regression model are used when combining into a single inference (the use of PROC MIANALYZE in step 3). Additionally, the standard errors (SE) for the odds ratios are transformed as follows:

$$SE = \frac{\log(UCL) - \log(LCL)}{2Z_{\alpha/2}} \tag{6}$$

Where UCL and LCL are the upper and lower confidence limit, respectively, for the confidence interval of the odds ratio from the logistic regression model, and $Z_{\alpha/2}$ is the relevant critical value from the standard normal distribution (1.96 for a 95% confidence interval). After the use of PROC MIANALYZE in step 4, the estimates of the log odds ratio for each bimekizumab dose relative to placebo and the corresponding upper and lower confidence limits will be provided. The odds ratio is estimated by exponentiating the estimate of the log odds ratio. The confidence limits of the odds ratio are then estimated as follows:

$$LCL = OR * \exp^{-(SE*Z_{a/2})}$$

$$UCL = OR * \exp^{(SE*Z_{a/2})}$$
(8)
Where OR is the back-transformed estimate of the odds ratio just described, SE is the standard

$$UCL = OR * \exp^{(SE*Z_{\alpha/2})}$$
 (8)

Where OR is the back-transformed estimate of the odds ratio just described, SE is the standard error of the log odds ratio derived in PROC MIANALYZE and $Z_{\alpha/2}$ is the relevant critical value from the standard normal distribution (1.96 for a 95% confidence interval). These calculations

Confidential Page 30 of 63 will be done such that odds ratios and corresponding confidence intervals are calculated for the odds ratio of each bimekizumab dose versus placebo. Note that the p-values presented in the tables will be the ones provided initially by PROC MIANALYZE and are not impacted by the transformations described above.

